4.1 Mosunetuzumab: Pharmaceutical and Therapeutic Background

Mosunetuzumab is a full-length, fully humanized IgG1 bispecific antibody that targets CD3 and CD20¹⁷. This can redirect T-cells to engage and eliminate CD20+ B-cells. This can lead to T-cell activation, cytokine elevation, and increase in tumor-infiltrating lymphocytes^{6,18}.

4.2 Polatuzumab vedotin: Pharmaceutical and Therapeutic Background

Polatuzumab vedotin, an ADC that delivers the microtubule inhibitor MMAE in a targeted fashion to cells expressing CD79b, is being evaluated as a replacement strategy in B-cell NHL for the microtubule inhibitor, vincristine. CD79b is a cell surface antigen that is expressed ubiquitously on large B-cell lymphoma tumor cells, as well as other mature B cells^{19,20}. The expression pattern of this surface antigen enables the application of polatuzumab vedotin in all mature B-cell lymphoma subtypes²⁰.

4.3 Rationale for Mosunetuzumab and Polatuzumab Vedotin with Obinutuzumab in Lymphoma

The most recent data of mosunetuzumab monotherapy in relapsed/refractory indolent NHL demonstrated an ORR and CR rate of 63% and 43% respectively⁶. These patients were examined with step-up dosing (i.e. 0.4/1.0/2.8 – 1.0/2.0/13.5mg, Cycle 1 Day 1/8/15). Grade 2 and 3 cytokine release syndrome was seen in 7.8% and 1.1% of patients, respectively⁶.

The safety and clinical activity of the antibody-drug conjugate polatuzumab vedotin in relapsed/refractory NHL was examined in a phase 1b/2 study¹⁰. Single agent polatuzumab vedotin was associated with objective responses in 23/42 (54.8%) evaluable patients in the dose-expansion cohort (2.4 mg/kg), including 7/42 (16.7%) complete responses (CR). There was an acceptable safety profile at the maximum tolerated dose, with the most common grade 3-4 toxicities being neutropenia (40%), anemia (11%), and peripheral sensory neuropathy (9%). In addition polatuzumab has been safely combined with obinutuzumab in relapsed/refractory follicular lymphoma with an overall response rate of 78%¹¹. The most common adverse events in > 20% of patients included fatigue (43%), diarrhea (34%), nausea (30%), constipation (21%), and headache (20%).

4.3.1 Rationale for Dose Selection/Regimen/Modification

Mosunetuzumab

Mosunetuzumab monotherapy has been examined in relapsed/refractory B-cell NHL⁶ as well as untreated DLBCL in patients unfit for standard treatment²¹.

Subcutaneous mosunetuzumab has been tested in a phase 1/1b with both flat dosing as well as step-up dosing [Matasar, 2020 #1294]. In the flat dosing cohort, patients were treated at 1.6 to 20 mg dose cohorts in a standard 3+3 design. A single DLT was observed at 1.6 mg (grade 4 neutropenia). Escalation otherwise proceeded without any other DLTs observed in other cohorts, and 26 patients treated at the final 20 mg dose. All CRS events across all cohorts were grade 1 (n=6, 26%) and grade 2 (n=2, 9%) and occurred during cycle 1. Efficacy in relapsed/refractory indolent NHL

patients were similar to results seen in the previously presented intravenous cohorts.

To further reduce the rate and severity of CRS events, and to improve patient convenience, mosunetuzumab SC step-up dosing regimens of 5/15/45 mg (F1) and 5/45/45 mg (F2) are being evaluated in Study GO29781 Group F. The C1D1 dose of 5 mg SC was selected as the projected C_{max} is similar to 1 mg IV, the recommended initial dose of the IV step-up dosing regimen. This starting dose of 5 mg was within the range evaluated in the Group D flat dosing schedule. The target dose was selected at 45 mg SC, as it is projected to provide a lower C_{max} (population pharmacokinetics [popPK] model predicted geometric mean ratio [GMR] = 0.37) but higher AUC ([GMR] = 1.49) at steady state than the 30 mg IV maintenance dose. Therefore, it is expected to be associated with sufficient exposure to drive anti-tumor activity with a potentially lower risk of CRS compared with Mosunetuzumab IV 1/2/60/30 mg dosing. Two different doses (15 mg and 45 mg) were evaluated on C1D8 to further evaluate step-up dosing for CRS mitigation to reach the target dose of 45 mg. The 5/45/45 mg dosing regimen showed comparable safety profiles to the 5/15/45 mg dosing regimen but with a shortened window of CRS associated mostly with only the first two doses of mosunetuzumab during cycle 1. Further, the 5/45/45 mg dosing regimen also allows faster achievement of target dose. Therefore, this dose is considered the preferred dose for mosunetuzumab SC monotherapy.

Polatuzumab vedotin combinations in B-cell NHL

Promising results led to the initiation of a phase 1b/2 clinical trial of polatuzumab vedotin in combination with R-CHP in DLBCL (R-CHOP with omission of vincristine)⁹. The MTD used in the combination regimen dose expansion cohort was 1.8 mg/kg. A recent update of this study found that the combination was well tolerated, with the most common grade 3-4 toxicities being neutropenia (30%), febrile neutropenia (18%), and thrombocytopenia (9%)⁹. Encouraging results in the dose expansion phase with high international prognostic index (IPI) patients led to the creation of a phase 3 randomized trial that has completed accrual comparing polatuzumab vedotin and R-CHP versus standard R-CHOP chemotherapy without known safety issues from a data safety monitoring committee (NCT03274492). The recommended dose of polatuzumab in this study was 1.8 mg/kg.

Polatuzumab vedotin has been safely combined with obinutuzumab in relapsed/refractory follicular lymphoma with an overall response rate of 78%¹¹. The most common adverse events in > 20% of patients included fatigue (43%), diarrhea (34%), nausea (30%), constipation (21%), and headache (20%).

In addition, polatuzumab vedotin was recently FDA approved in combination with rituximab and bendamustine for patients with DLBCL who have received 2 prior lines of therapy. The recommend polatuzumab vedotin dose to be given every 3 weeks in this regimen is also 1.8 mg/kg.

4.3.2 Rationale for Endpoints:

The primary endpoint is estimating the efficacy of this regimen as measured by the proportion of subjects who have achieved a complete response (CR) as the best response by the end of therapy.

4.3.2.1 Secondary/Exploratory Endpoints:

Secondary endpoint is estimating the end of treatment overall response rate.

Exploratory endpoints include estimating the PFS and OS for this combination using the appropriate response criteria for the histology tested. These also include stratifying ORR, CR, PFS, DOR, and OS by subjects receiving mosunetuzumab alone vs. mosunetuzumab followed by polatuzumab vedotin and obinutuzumab. Additional endpoints include estimating the safety of this regimen as measured by the frequency of adverse events (AEs) and correlating clinical outcomes including but not limited to ctDNA analysis, genomics, cytokine levels.

5.0 METHODOLOGY

Entry Criteria:

5.1 Subject Inclusion Criteria

In order to be eligible for participation in this trial, the subject must:

1. Diagnosis of indolent B-cell non-Hodgkin lymphoma with no prior systemic therapy. Eligible histologies based on 2016 WHO classification²² include:
 - a. Follicular lymphoma (Grade 1-2 or 3a)
 - b. Marginal zone lymphoma. Patients with MALT subtype of MZL may have relapsed or refractory disease after a course of antibiotic therapy.
2. Meet criteria for initiation of therapy that include one of the following
 - a. Symptomatic disease (including but not limited to pain/discomfort, b-symptoms)
 - b. Threatened end-organ function
 - c. Progressive cytopenias (Leukopenia (WBC < 1,000/uL) OR Hemoglobin < 10 g/dL OR platelets < 100,000/uL)
 - d. Steady progression

- e. Bulky disease (one site at least 7 cm or at least four sites of 3 cm)
- f. Hepatomegaly
- g. Splenomegaly
- 3. Be willing and able to provide written informed consent for the trial.
- 4. Have had an informed discussion with the investigator as part of the consenting/screening process that included information on treatments for these conditions with known clinical benefit, and there is documented understanding that the patient is forgoing approved available therapies.
- 5. Be ≥ 18 years of age on day of signing informed consent.
- 6. Have measurable FDG-avid nodal disease, including at least 1 disease site measuring at least 1.5 cm in longest dimension on CT or FDG-PET, or FDG-avid extra nodal measurable site measuring at least 1.0 cm in longest dimension.
- 7. Have a performance status of 0-2 on the ECOG Performance Scale (PS)
- 8. Demonstrate adequate organ function as defined in Table 1 below:

Table 1: Adequate Organ Function Laboratory Values

System	Laboratory Value
Hematological	
Absolute neutrophil count (ANC)	$\geq 1,000/\mu\text{L}$ except in cases of marrow infiltration by lymphoma
Platelets	$\geq 75,000 / \text{mCL}$ except in cases of marrow infiltration by lymphoma or hypersplenism
Hemoglobin	$\geq 8 \text{ g/dL}$ except in cases of marrow infiltration by lymphoma without red blood cell (RBC) transfusion within 14 days of first treatment
Renal	
Measured or calculated ^a creatinine clearance (GFR can also be used in place of creatinine or CrCl)	$\geq 40 \text{ mL/min}$
Hepatic	
Serum total bilirubin	$\leq 1.5 \text{ X ULN}$ (Patients with documented Gilbert disease may be enrolled if total bilirubin $\leq 3.0 \text{ x ULN}$) OR
	Direct bilirubin $\leq \text{ULN}$ for subjects with total bilirubin levels $> 1.5 \text{ ULN}$
AST (SGOT) and ALT (SGPT)	$\leq 2.5 \text{ X ULN}$ OR $\leq 5 \text{ X ULN}$ for subjects with liver involvement
Coagulation	
International Normalized Ratio (INR) or Prothrombin Time (PT)	$\leq 1.5 \text{ X ULN}$ unless subject is receiving anticoagulant therapy as long as PT or PTT is within therapeutic range of intended use of anticoagulants

Activated Partial Thromboplastin Time (aPTT)	≤1.5 X ULN unless subject is receiving anticoagulant therapy as long as PT or PTT is within therapeutic range of intended use of anticoagulants, or subject is shown to have an antiphospholipid antibody on workup
^a Creatinine clearance should be calculated per institutional standard.	

9. For women of childbearing potential: agreement to remain abstinent (refrain from heterosexual intercourse) or use contraceptive methods that result in a failure rate of ≤1% per year during the treatment period and for at least 3 months after the last dose mosunetuzumab or 6 months after the last dose of obinutuzumab. Women must refrain from donating eggs during this same period. A woman is considered to be of childbearing potential if she is post-menarcheal, has not reached a postmenopausal state (≤12 continuous months of amenorrhea with no identified cause other than menopause), and has not undergone surgical sterilization (removal of ovaries and/or uterus). The definition of childbearing potential may be adapted for alignment with local guidelines or requirements. Examples of contraceptive methods with a failure rate of ≤1% per year include bilateral tubal ligation, male sterilization, hormonal contraceptives that inhibit ovulation, hormone-releasing intrauterine devices, and copper intrauterine devices. The reliability of sexual abstinence should be evaluated in relation to the duration of the clinical trial and the preferred and usual lifestyle of the patient. Periodic abstinence (e.g., calendar, ovulation, symptothermal, or post-ovulation methods) and withdrawal are not acceptable methods of contraception
10. For women of childbearing potential, a negative serum pregnancy test result during screening period. Women who are considered not to be of childbearing potential are not required to have a pregnancy test.
11. For men: agreement to remain abstinent (refrain from heterosexual intercourse) or use a condom, and agreement to refrain from donating sperm, as defined below: With female partners of childbearing potential or pregnant female partners, men must remain abstinent or use a condom during the treatment period and for at least 5 months after the last treatment. Men must refrain from donating sperm during this same period. The reliability of sexual abstinence should be evaluated in relation to the duration of the clinical trial and the preferred and usual lifestyle of the patient. Periodic abstinence (e.g., calendar, ovulation, symptothermal, or postovulation methods) and withdrawal are not acceptable methods of preventing drug exposure. Male patients considering preservation of fertility should bank sperm before study treatment.
12. Patients on agents that modulate CYP3A4 listed in appendix 14.4 should be aware that these agents are prohibited if they require treatment in Part B, and require discontinuation for at least 5 half-lives in order to proceed with Part B.

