Subjects who must permanently discontinue mosunetuzumab monotherapy due to toxicity should have a response assessment with positron emission tomography (PET)/CT as soon as is clinically feasible and be evaluated for consideration of treatment in Part B as outlined below. These subjects would then be realigned to cycle 9 day 1 provided at least 21 days \pm 2 days have passed since the last mosunetuzumab injection

Subjects will undergo a computed tomography (CT) between cycle 4 day 1 and cycle 5 day 1. Those with at least stable disease (SD) or better by Lugano²³ criteria will proceed with treatment for cycles 5-8. Subjects with progressive disease (PD) at this timepoint may proceed with cycles 5-8 if the investigator assesses that the subject is deriving clinical benefit from the study medication (e.g. pseudoprogression). If there is no clinical benefit to this medication seen in patients with PD, subjects should receive additional therapy outside of the protocol.

Imaging with a PET/CT will be performed between cycle 8 day 1 and cycle 9 day 1. Subjects in a complete remission (CR) will not receive any further study therapy and will be observed in long term follow up. For this response assessment, a Deauville score will be assigned by the clinical radiology read. If the sub-investigator or principal investigator disagrees with the Deauville score assigned, another nuclear medicine physician will adjudicate the results.

All other subjects who do not achieve a CR may proceed with Part B of study treatment. Those with progressive disease (PD) may proceed with Part B only if they are deriving clinical benefit from the treatment (e.g., pseudoprogression, mixed response overall reduction in tumor) after discussion with the Principal Investigator.

Mosunetuzumab Dose Modifications/Toxicity Management

Administration of mosunetuzumab will be performed in a clinical setting with immediate access to a code team staff who are trained to monitor for and respond to medical emergencies. Additional management may take place after transfer to the University of Washington Medical Center, where there is access to neurology and nephrology consultation services in the event of cytokine release syndrome and tumor lysis syndrome, respectively.

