14.3 Response Criteria: “The Lugano Classification”³⁸

Response and Site	PET-CT–Based Response	CT-Based Response
Complete	Complete metabolic response	Complete radiologic response (all of the following)
Lymph nodes and extralymphatic sites	Score 1, 2, or 3* with or without a residual mass on 5PS†	Target nodes/nodal masses must regress to ≤ 1.5 cm in LD _i
	It is recognized that in Waldeyer's ring or extranodal sites with high physiologic uptake or with activation within spleen or marrow (eg, with chemotherapy or myeloid colony-stimulating factors), uptake may be greater than normal mediastinum and/or liver. In this circumstance, complete metabolic response may be inferred if uptake at sites of initial involvement is no greater than surrounding normal tissue even if the tissue has high physiologic uptake	No extralymphatic sites of disease
Nonmeasured lesion	Not applicable	Absent
Organ enlargement	Not applicable	Regress to normal
New lesions	None	None

Response and Site	PET-CT–Based Response	CT-Based Response
Bone marrow	No evidence of FDG-avid disease in marrow	Normal by morphology; if indeterminate, IHC negative
Partial	Partial metabolic response	Partial remission (all of the following)
Lymph nodes and extralymphatic sites	Score 4 or 5 ⁺ with reduced uptake compared with baseline and residual mass(es) of any size	≥ 50% decrease in SPD of up to 6 target measurable nodes and extranodal sites
	At interim, these findings suggest responding disease	When a lesion is too small to measure on CT, assign 5 mm × 5 mm as the default value
	At end of treatment, these findings indicate residual disease	When no longer visible, 0 × 0 mm
		For a node > 5 mm × 5 mm, but smaller than normal, use actual measurement for calculation
Nonmeasured lesions	Not applicable	Absent/normal, regressed, but no increase
Organ enlargement	Not applicable	Spleen must have regressed by > 50% in length beyond normal
New lesions	None	None
Bone marrow	Residual uptake higher than uptake in normal marrow but reduced compared with baseline (diffuse uptake compatible with reactive changes from chemotherapy allowed). If there are persistent focal changes in the marrow in the context of a nodal response, consideration should be given to further evaluation with MRI or biopsy or an interval scan	Not applicable
No response or stable disease	No metabolic response	Stable disease

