- * A score of 3 in many patients indicates a good prognosis with standard treatment, especially if at the time of an interim scan. However, in trials involving PET where de-escalation is investigated, it may be preferable to consider a score of 3 as inadequate response (to avoid undertreatment). Measured dominant lesions: Up to six of the largest dominant nodes, nodal masses, and extranodal lesions selected to be clearly measurable in two diameters. Nodes should preferably be from disparate regions of the body and

should include, where applicable, mediastinal and retroperitoneal areas. Non-nodal lesions include those in solid organs (eg, liver, spleen, kidneys, lungs), GI involvement, cutaneous lesions, or those noted on palpation. Nonmeasured lesions: Any disease not selected as measured, dominant disease and truly assessable disease should be considered not measured. These sites include any nodes, nodal masses, and extranodal sites not selected as dominant or measurable or that do not meet the requirements for measurability but are still considered abnormal, as well as truly assessable disease, which is any site of suspected disease that would be difficult to follow quantitatively with measurement, including pleural effusions, ascites, bone lesions, leptomeningeal disease, abdominal masses, and other lesions that cannot be confirmed and followed by imaging. In Waldeyer's ring or in extranodal sites (eg, GI tract, liver, bone marrow), FDG uptake may be greater than in the mediastinum with complete metabolic response, but should be no higher than surrounding normal physiologic uptake (eg, with marrow activation as a result of chemotherapy or myeloid growth factors).

- ¶ PET 5PS: 1, no uptake above background; 2, uptake \leq mediastinum; 3, uptake $>$ mediastinum but \leq liver; 4, uptake moderately $>$ liver; 5, uptake markedly higher than liver and/or new lesions; X, new areas of uptake unlikely to be related to lymphoma.

14.4 **Table 11:** List of CYP3A4 inhibitors/inducers and P-gp inhibitors

	Strong inhibitors	Moderate inhibitors	Weak inhibitors

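### Entry sets no uptake level for FDG-avid disease, but PET-based CR is an absolute score, so a subject with uniformly low baseline uptake can be scored CR on an unchanged scan

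*Combined protocol and SAP*

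**What the plan says.** **Entry.** Section 5.1, item 6 reads "Have measurable FDG-avid nodal disease, including at least 1 disease site measuring at least 1.5 cm in longest dimension on CT or FDG-PET". The alternative route is an "FDG-avid extra nodal measurable site measuring at least 1.0 cm in longest dimension". Neither ties avidity to mediastinum, liver or a 5PS score. Item 2 is a separate requirement: "Meet criteria for initiation of therapy that include one of the following", followed by symptoms, threatened organs, cytopenias, steady progression, bulk, and liver or spleen enlargement.

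**Response.** In Appendix 14.3 the PET-based CR entry for nodes and extralymphatic sites is "Score 1, 2, or 3* with or without a residual mass on 5PS". The footnote defines score 1 as "no uptake above background", score 2 as up to mediastinum, score 3 as above mediastinum and up to liver, and scores 4 and 5 as above liver. PET-based CR also needs a marrow free of avid disease and no new lesions. The CT-based CR is a list of conditions that must all be met. The nodal one is "Target nodes/nodal masses must regress to ≤ 1.5 cm".

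**Use of the result.** CR as best response is the primary endpoint (Section 3.0). After cycle 8 it also decides treatment (Section 5.3): "Subjects in a complete remission (CR) will not receive any further study therapy and will be observed in long term follow up". Section 5.3 has the radiology read assign a Deauville score to that scan. Baseline PET/CT with diagnostic CT is mandatory (Sections 6.1 and 7.1.2.5), but no baseline score is asked for. Section 8.0 calls the study successful at 34 or more CRs among 42.

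**The concern.** Entry and response use different yardsticks for uptake. Entry uses an undefined adjective, and response uses a fixed threshold at liver. Where a reader applies the adjective to uptake at or below liver, a subject can enter the trial already on the CR side of that threshold. A CR recorded later then carries no information about treatment effect.

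Two things depend on that call. The primary endpoint is judged on a point estimate against 80%, so every automatic CR pushes toward success. The same call also stops study therapy after cycle 8 in a subject whose disease may be unchanged.

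**Working it through.** **Step 1. Where can an unchanged low-uptake subject fall?** Take a subject whose sites all score 2 or 3 at baseline, with no avid marrow. Suppose the post-cycle-8 PET/CT is identical. The PET column of Appendix 14.3 gives:

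| Category | What it needs | Met? |
|---|---|---|
| CR | Score 1 to 3, residual mass allowed, no new lesions, no avid marrow | Yes |
| PR | Score 4 or 5, reduced from baseline | No |
| Stable disease | Score 4 or 5, not significantly changed | No |
| Progression | Score 4 or 5 with increased uptake, or new avid foci | No |

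CR is the only category left. The condition applies to the whole subject: one site at 4 or 5, or avid marrow, removes it.

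**Step 2. Does the size limit create the same problem?** Nodal entry starts at 1.5 cm and CT-based CR ends at 1.5 cm, so the two touch only at exactly 1.5 cm. For an unchanged subject to be CR by CT, no node may exceed 1.5 cm, every other CT condition must already be normal, and the requirement to regress must be read as a bare threshold. On PET/CT, node size does not decide CR. The issue is therefore confined to the CT-only assessments after cycles 4 and 11. The 1.0 cm extranodal route cannot meet CT-based CR at baseline, because that column allows no extralymphatic disease.

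**Step 3. Reproduce the plan's table.** Inputs from Section 8.0 are n = 42 and success at 34 or more (0.8 × 42 = 33.6, rounded up). The formula is P(X ≥ 34) with X ~ Binomial(42, p).

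| True CR rate p | .65 | .70 | .75 | .80 | .85 | .90 |
|---|---|---|---|---|---|---|
| Plan | .02 | .08 | .24 | .53 | .83 | .98 |
| Recomputed | .019 | .080 | .243 | .531 | .831 | .979 |

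The plan's table is reproduced.

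**Step 4. Add k automatic CRs.** The documents give no value for k, so k = 0 to 4 is an assumption. All 42 subjects are taken as evaluable. The remaining 42−k subjects respond independently at rate p and must supply 34−k CRs, so the probability is P(X ≥ 34−k) with X ~ Binomial(42−k, p).

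| k | p = .70 | p = .75 | p = .80 |
|---|---|---|---|
| 0 | .080 | .243 | .531 |
| 1 | .094 | .270 | .562 |
| 2 | .111 | .300 | .593 |
| 3 | .130 | .331 | .624 |
| 4 | .152 | .365 | .655 |

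**Step 5. Bias in the CR rate itself.** Without the loophole such a subject would be a CR with probability p. With it, the probability is 1. The expected gain per subject is (1−p)/42.

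- At p = 0.75: 0.25/42 = 0.6 percentage points.
- At p = 0.70: 0.30/42 = 0.7 percentage points.
- Four subjects at p = 0.75: 4 × 0.25/42 = 2.4 percentage points in total.

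**The case against.** The strongest reply is that the overlap is possible rather than shown. Appendix 14.3 itself uses avidity for active disease: avid marrow rules out CR, and new avid foci mean progression. A reader following that usage might never call uptake at or below liver avid at entry. The argument is fair, and k may be zero. But item 6 does not say so, and the appendix gives no threshold for the word either.

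The second reply is that safeguards exist. The investigator reviews PET/CT images and disagreements are adjudicated (Sections 5.3 and 7.1.2.5). The concurrent CT would show an unchanged mass. Equivocal findings call for biopsy or repeat imaging (Section 7.1.6.3), and marrow is examined at CR when indicated, although this can be waived (Section 7.1.2.6). These make an unnoticed error less likely. None addresses the scoring rule: a clear score of 2 or 3 is not equivocal, adjudication concerns the score rather than its change from baseline, and a residual mass is explicitly compatible with PET-based CR.

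Third, this is a pilot with no powered hypothesis, its 80% is described as a loose benchmark, and other endpoints and toxicity will be weighed. That limits the consequence but does not remove the bias.

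A reader might also infer that a 1.5 cm node already satisfies CR at baseline, or that the size and avidity item is the only disease-related entry hurdle. The documents support neither. Step 2 disposes of the first. On the second, item 2 must also be met, and bulk or organ enlargement there would be incompatible with CT-based CR. Symptoms or steady progression would not be, so item 2 does not close the uptake gap.

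**Conclusion.** The point holds for uptake. The current text allows one specific kind of subject to be scored CR without any response: every site at or below liver at baseline, no avid marrow, no new lesions. It rests on a reader accepting such uptake as avid at entry.

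The direction is certain, toward success. The size is not. At p = 0.75 each such subject adds about 0.6 points in expectation, and the chance of meeting the benchmark rises from 0.243 to 0.270, 0.300, 0.331 and 0.365 for one to four subjects. It might be inferred that each adds the full 1/42 = 2.4 points. That would require that none of them could otherwise have reached CR, which nothing in the documents supports. Nor do the documents say how many subjects are affected or which histology they would have.

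The 1.5 cm limits are a minor mismatch, not a second route to an automatic CR. The change is worth making because it is cheap and removes a one-sided error from the primary endpoint.

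**What to change.** 1. Record a baseline 5PS score for each subject from the mandatory screening PET/CT (Section 7.1.2.5).
2. For future enrolment, define FDG-avid in Section 5.1, item 6 as a 5PS score of 4 or 5 in at least one measurable site.
3. In Section 8.0, state that for the primary endpoint a PET score of 1 to 3 does not count as CR in a subject whose highest baseline score is 3 or less. Assess that subject by the CT column of Appendix 14.3. Specify this before analysis and apply it as an endpoint-scoring rule.
4. The sponsor should reconcile the scoring rule with the Section 5.3 rule that CR ends study therapy, since a subject could then be CR under one and not the other. How treatment should follow is for the sponsor to settle.
5. As a minor alignment, set nodal entry above 1.5 cm, to match the size at which Appendix 14.3 treats a node as abnormal. This matters only at exactly 1.5 cm on CT-only assessments.

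The cost is a short amendment with no new scan or reader, because baseline PET/CT and the concurrent diagnostic CT are already required. A few low-uptake subjects would become ineligible or be scored by CT, and the observed CR rate may be slightly lower. Changing an endpoint rule during an open-label study carries its own risk of bias. The baseline scores should therefore be read, and the rule fixed, without reference to outcomes.
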